9.6.9. Physical Examination

A full physical examination will be performed at Screening according to the Time and Events Schedule. Limited physical examinations of involved organs will be performed at subsequent visits as outlined in the cohort-specific Time and Events Schedule. Clinically significant abnormalities should be reported as AEs.

9.6.10. ECOG Performance Status

ECOG PS Grade will be determined at pre-specified timepoints listed in the cohort-specific Time and Events Schedule. ECOG scoring information is provided in [Attachment 3](#).

9.6.11. Documentation of Hearing Loss

For subjects enrolled in the Phase 2 part of the study, documentation of Grade 2 or higher hearing loss is required for cis-ineligible subjects if hearing loss is the single reason for cis-ineligibility. Audiometry may be performed, or prior audiometry test results must be available for review. In subjects already using hearing aid, documentation of the use of a hearing aid is sufficient for this requirement. Audiometry tests that were performed prior to consent for the full-study was obtained is permitted to be collected as long as it is documented this procedure was performed as part of standard of care and not specifically for study purposes.

9.7. Sample Collection and Handling

The actual dates and times of sample collection must be recorded in the laboratory requisition form/source documentation. Refer to the cohort-specific Time and Events Schedules for the timing and frequency of all sample collections.

Instructions for the collection, handling, and shipment of samples are found in the Laboratory Manual.

10. SUBJECT COMPLETION/DISCONTINUATION OF STUDY TREATMENT/ WITHDRAWAL FROM THE STUDY

Following Amendment 5, once the end of study data collection timepoint has been reached, the eCRF will be closed and only SAEs must be reported through the company safety repository.

10.1. Completion

Prior to Protocol Amendment 5, a subject will be considered as having completed the study if he or she has died before the end of the study or has not been withdrawn from the study by the end of the study (see Section 10.2). Following Amendment 5, once the end of study data collection timepoint has been reached, subjects who continue to benefit from study treatment(s), as determined by their investigator, may continue to receive access to study treatment(s) on this study, with reduced data collection (see Section 17.9.1), either via a long term extension roll-over study or any other post-trial access program, when permitted by local regulations. Provision may continue until the subject can commercially access study treatment(s) within the local healthcare system, until a decision is made not to pursue the studied indication, until the investigator decides it is in the best interest of the subject that study treatment(s) be discontinued, or until 2 years after local marketing authorization for is obtained for the studied indication, whichever comes first.

Once the end of study data collection timepoint has been reached, subjects who have discontinued study treatment(s), and all ongoing subjects in the Follow-up Phase will be considered to have completed the study (see Section 17.9.1 for definition of end of study data collection).

10.2. Discontinuation of Study Treatment/Withdrawal from the Study

Discontinuation of Study Treatment

A subject who discontinued treatment will be followed up for recovery of AEs for subsequent therapies and survival.

A subject's study treatment must be discontinued if:

- The investigator believes that for safety reasons or tolerability reasons (eg, AE) it is in the best interest of the subject to discontinue study treatment
- The subject has met any of the criteria listed in Sections 6.2.2 or 6.3.3
- The subject becomes pregnant
- Disease progression

- Exception: if the investigator and medical monitor agree that continuation of treatment is in the best interest of the subject considering the terminal nature of the underlying disease, he/she may receive treatment until such time as the treating physician and the medical monitor agree that further continuation of treatment is no longer beneficial to the subject
- Unacceptable toxicity
- The subject refuses further treatment with the study drug
- The sponsor terminates the study
- Investigator decision approved by the sponsor

If a subject discontinues study treatment for any reason before the end of the Treatment Phase, an End-of-Treatment Visit should be completed, and posttreatment assessments should be obtained and scheduled assessments should be continued.

Withdrawal From the Study

A subject will be withdrawn from the study for any of the following reasons:

- Lost to follow-up
- Withdrawal of consent

If a subject is lost to follow-up, every reasonable effort must be made by the study-site personnel to contact the subject and determine the reason for discontinuation/withdrawal. The measures taken to follow-up must be documented.

When a subject withdraws before completing the study, the reason for withdrawal is to be documented in the eCRF and in the source document. Study drug assigned to the withdrawn subject may not be assigned to another subject. Subjects may be replaced if 1 of the following criteria is met:

- The subject withdraws prior to the study drug administration.
- The subject is not evaluable for DLT (For the Phase 1b erdafitinib + cetrelimab cohort, refer to Section 3.3.1 of Appendix 1. For the Phase 1b erdafitinib + cetrelimab + platinum chemotherapy cohort, refer to Section 3.3.1 of Appendix 2.)

10.3. Withdrawal From the Use of Research Samples

The subject may withdraw consent for use of samples for research (refer to Section 16.2.5, Long-Term Retention of Samples for Additional Future Research). In such a case, samples will be destroyed after they are no longer needed for the clinical study. Details of the sample retention for research are presented in the Full-Study ICF.

11. STATISTICAL METHODS

Statistical analysis will be done by the sponsor or under the authority of the sponsor. A general description of the statistical methods to be used to analyze the efficacy and safety data is outlined below. Specific details will be provided in the Statistical Analysis Plan.

11.1. Sample Size Determination

This is a Phase 1b-2 study comprised of a Phase 1b dose escalation part and a Phase 2 dose expansion cohort. The sample size of each phase is calculated as described in Sections 11.1.1 and Section 11.1.2.

11.1.1. Sample Size - Phase 1b

The total number of subjects to be enrolled in Phase 1b will depend on the dose level at which DLT of the combination are met or the RP2D is determined. Once a dose level is opened for enrollment, subjects will be entered in groups of 3 unless otherwise clinically indicated. A minimum of 6 subjects will be treated at a dose level or at the next higher level before the dose level can be declared as the RP2D. The expected number of subjects to be enrolled in the Phase 1b erdafitinib + cetrelimab cohort is 12 to 30.

A total of approximately 40 subjects will be enrolled in the Phase 1b erdafitinib + cetrelimab + platinum (cisplatin or carboplatin) chemotherapy cohort. Three subjects (either wild-type or with select FGFR gene alterations) will be enrolled in the initial erdafitinib + cetrelimab + cisplatin dose level (50 mg/m^2). If the starting dose is safe, 6 additional subjects will be enrolled into the escalated dose of cisplatin (60 mg/m^2). Out of 6 subjects, up to 3 subjects can be wild-type and the other subjects should be with select FGFR gene alterations. Wild-type is defined as subjects without FGFR gene alteration and subjects with FGFR gene alterations other than the select FGFR alterations as described in Table 4. Approximately 10 additional subjects with select FGFR gene alterations will be enrolled at the MTD for erdafitinib + cetrelimab + cisplatin.

Three subjects (either wild-type or with select FGFR gene alterations) will be enrolled in the initial erdafitinib + cetrelimab + carboplatin dose level ($\text{AUC}4 \text{ mg/mL/min}$). If the starting dose is safe, 6 additional subjects will be enrolled into the escalated dose of carboplatin ($\text{AUC}5 \text{ mg/mL/min}$). Out of 6 subjects, up to 3 subjects can be wild-type and the other subjects should be with select FGFR gene alterations. Approximately 10 additional subjects with select FGFR gene alterations will be enrolled at the MTD for erdafitinib + cetrelimab + carboplatin.

11.1.2. Sample Size - Phase 2

In Phase 2, approximately 90 subjects will be assigned randomly in a 1:1 ratio to receive either erdafitinib monotherapy treatment (Arm A) or erdafitinib and cetrelimab combination therapy (Arm B).

- 1) In the erdafitinib monotherapy arm (Arm A), ORR will be estimated using a 95% confidence interval. Assuming a true ORR of 45%, a sample size of approximately 45 subjects will result in a 95% confidence interval that excludes those less than or equal to 30%.
- 2) In the erdafitinib and cetrelimab combination therapy (Arm B), ORR will be estimated using a 95% confidence interval. Assuming a true ORR of 55%, a sample size of approximately 45 subjects result in a 95% confidence interval that excludes ORR less or equal to 40%.

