Approximately 40 subjects will be enrolled in the erdafitinib + cetrelimab + platinum (cisplatin or carboplatin) chemotherapy cohort. In Phase 2, approximately 90 subjects will be assigned randomly in a 1:1 ratio to receive either erdafitinib monotherapy (Arm A) or erdafitinib and cetrelimab combination therapy (Arm B). With approximately 45 subjects on Arm A and assuming a true ORR of 45%, the study is designed such that the resulting 95% confidence interval for estimating ORR excludes those less or equal to 30%. Similarly, assuming a true ORR of 55% in Arm B, approximately 45 subjects results in a 95% confidence interval that excludes ORR less or equal to 40%. The objective response rate will be calculated with a 95% confidence interval by each arm in the treated population according to the RECIST 1.1 criteria ([Attachment 9](#)). Safety data will be summarized descriptively.

The primary efficacy analysis is planned with ~6 months of follow-up from last patient enrolled or sooner (if last patient discontinued prior to the 6-month follow-up). This will be the final analysis for the study. The primary efficacy analysis will be based on the response assessed by investigators.

TIME AND EVENTS SCHEDULE

The Time and Events Schedule for the Phase 1b erdafitinib + cetrelimab cohort can be found in the [Appendix 1 Table 1](#).

The Time and Events Schedule for the Phase 1b erdafitinib + cetrelimab + platinum chemotherapy cohort can be found in [Appendix 2 Table 1](#).

The Time and Events Schedule for the Phase 2 erdafitinib + cetrelimab +/- cohort of the study can be found in [Appendix 3 Table 1](#).

The Time and Events Schedule for the Phase 1b and Phase 2 cohorts after the end of study data collection timepoint has been achieved can be found in [APPENDIX 4](#) Table 1.

ABBREVIATIONS

ADL	Activities of daily living
AE	adverse event
AJCC	American joint committee on cancer
ALT	alanine aminotransferase
ANC	absolute neutrophil count
AST	aspartate aminotransferase
AUC	area under the concentration curve
BSA	body surface area
BUN	Blood urea nitrogen
carbo	carboplatin
cet	cetrelimab
chemo	chemotherapy
CI	confidence interval
cis	cisplatin
C _{max}	maximum serum concentration
C _{min}	minimum serum concentration
CR	complete response
CSR	central serous retinopathy
CT	computed tomography
ctDNA	circulating tumor DNA
CYP	cytochrome P450
DCF	data clarification form
DCR	disease control rate
DDI	drug-drug interaction
DILI	drug induced liver-injuries
DL	dose level

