11.4. Efficacy Analyses (Phase 2 Only)

The primary efficacy analysis is planned with ~6 months of follow-up from last patient enrolled or sooner (if last patient discontinued prior to the 6-month follow-up). This will be the final analysis for the study. The primary efficacy analysis will be based on the response assessed by investigators. After the end of study data collection timepoint has been achieved, no further efficacy data will be collected on the eCRF.

To explore the clinical activity of erdafitinib or erdafitinib in combination with cetrelimab in Phase 2, the following efficacy analyses will be performed by each arm in the treated population according to the RECIST 1.1 criteria:

- Primary endpoint: ORR will be estimated with a 95% confidence interval. The primary efficacy analysis will be based on the response assessed by investigators.
- Secondary endpoints: TTR will be summarized descriptively based on responders. The Kaplan-Meier method will be used to estimate the distribution of DoR based on responders. The distributions of PFS and OS will be summarized using similar Kaplan-Meier estimates.

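### Section 11.1.2 and the Synopsis state as a certain result a CI exclusion that has only about even odds at 45 subjects per arm

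*Protocol*

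**What the plan says.** Section 11.1.2 (Sample Size - Phase 2) plans about 90 subjects randomised 1:1 and justifies about 45 per arm in two items.

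- **Arm A.** The premise is "Assuming a true ORR of 45"%. The stated consequence is that "a sample size of approximately 45 subjects will result in a 95% confidence interval that excludes those less than or equal to 30"%.
- **Arm B.** The premise is a true ORR of 55%. The stated consequence is that "a sample size of approximately 45 subjects result in a 95% confidence interval that excludes ORR less or equal to 40"%.

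The Synopsis (Statistical Methods) repeats both. For Arm A, "the study is designed such that the resulting 95% confidence interval for estimating ORR excludes those less or equal to 30"%. For Arm B, "approximately 45 subjects results in a 95% confidence interval that excludes ORR less or equal to 40"%.

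All four sentences start from a true rate and give the exclusion as what follows from it. None attaches a probability, and none refers to an observed or expected rate. Section 11.4 describes the analysis only as estimation by arm: "Primary endpoint: ORR will be estimated with a 95% confidence interval".

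**The concern.** A confidence interval is built from the observed response rate, which varies around the true rate. If the sample size is chosen so that the lower limit falls just above the bound when the observed rate equals the assumed rate, the bound is excluded only when the observed rate comes out at about the assumed rate or higher. That happens roughly half the time when the assumption is exactly right. The four sentences present this outcome as assured.

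This is the only quantitative basis the protocol gives for 45 subjects per arm. A reader would take it that 30% and 40% will be excluded provided the assumed ORRs are true. If one arm's lower limit then fell below its bound, the same reader could wrongly infer that the assumed ORR had not been met.

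**Working it through.** **Inputs.** n = 45 per arm, true ORR 45% (Arm A) or 55% (Arm B), bounds 30% and 40% (Section 11.1.2 and Synopsis); 95% CI, each arm separately (Section 11.4). The protocol names no CI method, so three standard ones are shown.

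**Step 1: reproduce the plan's figure.** Put the assumed rate into the Wald lower limit, p − 1.96·√(p(1 − p)/n):

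- Arm A: 0.45 − 1.96·√(0.45·0.55/45) = 0.45 − 0.145 = 0.305
- Arm B: 0.55 − 1.96·√(0.55·0.45/45) = 0.55 − 0.145 = 0.405

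Both clear their bounds, and the smallest n that does so is 43 in each arm. The figure of 45 therefore reproduces, but only with the observed rate set equal to the assumed rate.

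**Step 2: find the smallest responder count r out of 45 whose lower limit exceeds the bound.**

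**Step 3: compute the exact binomial probability P(X ≥ r | n = 45, true ORR).**

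| Arm | CI method | r | Lower limit at r | P(X ≥ r) |
|---|---|---|---|---|
| A (true 45%, bound 30%) | Wald | 21 | 32.1% | 0.468 |
| A | Clopper-Pearson | 21 | 31.7% | 0.468 |
| A | Wilson | 20 | 30.9% | 0.587 |
| B (true 55%, bound 40%) | Wald | 25 | 41.0% | 0.532 |
| B | Wilson | 25 | 41.2% | 0.532 |
| B | Clopper-Pearson | 26 | 42.2% | 0.413 |

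**Step 4: allow for the word approximately.** Repeating steps 2 and 3 for n = 43 to 47 with the same three methods gives 0.468 to 0.637 in Arm A and 0.399 to 0.595 in Arm B.

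**Step 5: both arms together.** Treating the arms as independent, the probability that both bounds are excluded at n = 45 is:

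- Clopper-Pearson: 0.468 × 0.413 = 0.19
- Wald: 0.468 × 0.532 = 0.25
- Wilson: 0.587 × 0.532 = 0.31

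**Step 6: scale.** For the exclusion probability to reach 80% and stay there would take about 81 to 88 subjects in Arm A and 89 to 94 in Arm B, depending on the method. This shows the size of the overstatement; it is not a proposal to enlarge the trial.

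**Precision actually delivered.** The 95% CI half-width at 20/45 or 25/45 is 13.9 points (Wilson), 14.5 (Wald) or 15.2 (Clopper-Pearson).

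**The case against.** The best defence is that this is an estimation design and the sentences are shorthand for expected precision. Each item in Section 11.1.2 opens by saying that ORR will be estimated with a CI, Section 11.4 sets out only estimation by arm, and the amendment log shows that hypotheses and power were deliberately removed in Amendment 3. On that reading 45 is a correct precision calculation, and no stated number is wrong.

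Part of this stands: the calculation behind 45 is sound for what it computes, and the fault lies in what the text says it delivers. The shorthand reading still fails, for two reasons. The text conditions on the true ORR, not the observed one. And the reading is fragile even on its own terms: 45% of 45 is 20.25 subjects, and at the nearest attainable count, 20/45, the lower limit is 29.9% (Wald) or 29.6% (Clopper-Pearson), so 30% is not excluded. In Arm B the Clopper-Pearson limit at 25/45 falls just under 40%.

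Two further objections are fair in part. The choice of CI method may properly sit in the SAP, and its absence here is not faulted; but none of the three methods makes the sentences true. It is also true that nothing depends on the exclusion: neither 30% nor 40% enters a test, success criterion or stopping rule. That limits the weight of the point but does not make the statement correct.

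**Conclusion.** The concern holds. The protocol credits its Phase 2 sample size with a property it does not have. At n = 45, with the assumed ORRs exactly true, the 95% CI excludes the bound with probability 47% to 59% in Arm A and 41% to 53% in Arm B, depending on the CI method. Nowhere does the protocol qualify the claim.

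These figures rest on independent binomial responses, 45 subjects analysed per arm, and a two-sided 95% interval by Wald, Wilson or Clopper-Pearson. The error is confined to the justification of the sample size; the planned analysis is unaffected. It should be fixed.

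**What to change.** Keep n. In the two sentences of Section 11.1.2 and the two in the Synopsis, remove the wording that makes the exclusion a consequence of the true rate. Replace it with a precision statement and the actual probability, for example:

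> With approximately 45 subjects per arm, the 95% CI half-width is about 14 to 15 percentage points at an observed ORR near 45% or 55%. If the true ORR in Arm A is 45%, the probability that the lower limit exceeds 30% is about [47% (at least 21 of 45 responders) for Wald or Clopper-Pearson; 59% (at least 20) for Wilson]. If the true ORR in Arm B is 55%, the probability that the lower limit exceeds 40% is about [53% (at least 25) for Wald or Wilson; 41% (at least 26) for Clopper-Pearson].

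Keep only the bracketed figure for the method the analysis will use, and make clear that the responder counts are not success thresholds. If the method is to stay in the SAP, a smaller repair also removes the false assurance: say that if the observed ORR is about 45% (55%), the lower 95% limit is about 30% (40%).

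The cost is four reworded sentences. Sample size, endpoint, population and analysis do not change; the stated property of the sample size becomes less favourable.

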11.2. Dose Escalation (Phase 1b)

A Modified Toxicity Probability Interval method, mTPI-2, will guide the dose escalation and RP2D recommendation in Phase 1b. In the mTPI-2 method, a decision theoretical framework links the dose-finding decisions of “Stay”, “De-escalation”, and “Escalation” with the equivalence interval $(p_T - \varepsilon_1, p_T + \varepsilon_2)$, over-dosing interval(s), and under-dosing interval(s), respectively. In this study, we use $p_T = 0.33$ and $\varepsilon_1 = \varepsilon_2 = 0.05$, the equivalence interval is $(0.28, 0.38)$. The interval, which has the largest posterior probability divided by the length of the interval, is selected as the winning interval and the dose-finding recommendation can be set correspondingly. At the end of Phase 1b, the estimated MTD is the dose with the smallest difference between the transformed posterior mean of p_d and p_T and among all the doses d . The detailed dose escalation guidelines for this study are outlined in and the SET charter. However, dose selection for the next cohort and the decision for RP2D are described in Section 3.3.

11.3. Analysis Populations

The analysis populations for the Phase 1b dose escalation part of the study are defined as the following:

- The Treated Population will consist of all subjects who receive at least 1 dose of study drug(s).
- DLT Evaluable Population: This set consists of all DLT evaluable subjects (defined in Section 3.3.1) among the treated population.

The analysis populations for the Phase 2 dose expansion part of the study are defined as the following:

- The Treated Population will consist of all subjects who receive at least 1 dose of study drug(s). The Treated Population will be used for all safety analyses and for efficacy analysis unless otherwise specified in the Statistical Analysis Plan.
- The PK/PD Population will consist of all subjects who received at least 1 dose of study drug(s) and have at least 1 during treatment sample collected to determine the concentration or PD biomarker response.

Subgroup analyses will be performed as appropriate, and details will be specified in the Statistical Analysis Plan.

11.4. Efficacy Analyses (Phase 2 Only)

The primary efficacy analysis is planned with ~6 months of follow-up from last patient enrolled or sooner (if last patient discontinued prior to the 6-month follow-up). This will be the final analysis for the study. The primary efficacy analysis will be based on the response assessed by investigators. After the end of study data collection timepoint has been achieved, no further efficacy data will be collected on the eCRF.

To explore the clinical activity of erdafitinib or erdafitinib in combination with cetrelimab in Phase 2, the following efficacy analyses will be performed by each arm in the treated population according to the RECIST 1.1 criteria:

- Primary endpoint: ORR will be estimated with a 95% confidence interval. The primary efficacy analysis will be based on the response assessed by investigators.
- Secondary endpoints: TTR will be summarized descriptively based on responders. The Kaplan-Meier method will be used to estimate the distribution of DoR based on responders. The distributions of PFS and OS will be summarized using similar Kaplan-Meier estimates.

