Erdafitinib monotherapy demonstrated efficacy in a subset of mUC patients without prior systemic therapy treated in a separate Phase 2 Global Open-Label Study 42756493BLC2001 of the efficacy and the safety of erdafitinib in subjects with metastatic or surgically unresectable urothelial cancer with FGFR genomic alterations ([Loriot 2019](#)). In that study, 10 cisplatin-ineligible patients with urothelial cancer who had no prior lines of systemic therapy in the metastatic setting were enrolled. In these 10 patients, median progression-free survival was 9.82 months (95% confidence interval [CI]: 1.38, 15.90) and median overall survival was 18.14 months (95% CI: 8.74, not evaluable). This efficacy with erdafitinib is comparable with standard front-line chemotherapy combination treatments albeit with fewer hematologic toxicities. The median overall survival was 13.8 months (95% CI, 12.3, 15.8) with gemcitabine and cisplatin and 14.8 months (95% CI, 13.2, 16.8) with

MVAC ([Von der Maase 2000](#)). In another study, median survival was 15.1 months on HD-MVAC and 14.9 months on M-VAC ([Sternberg 2006](#)). With gemcitabine and carboplatin, a median OS of 9.3 months has been reported ([DeSantis 2012](#)). Among all mUC patients, irrespective of PD1 status, a median overall survival of 15.9 months (95% CI, 10.4, not estimable) with atezolizumab ([Balar 2017](#)) and a median OS of 11.5 months (95% CI, 10.0, 13.3) with pembrolizumab ([Balar 2018](#)) have been reported.

Based on the above data from BLC2001, cisplatin-ineligible patients with select FGFR alterations without prior systemic therapy are anticipated to have a beneficial effect from erdafitinib monotherapy. The combination of erdafitinib + cetrelimab (Arm B) is designed to estimate if and how much additive efficacy effect may be obtained with comparable or additional safety events.

CCI

.

Randomization in Phase 2 helps in reducing bias when interpreting the efficacy and safety data in each arm. Analyses of safety and efficacy will be performed by each arm when there are approximately 90 response-evaluable subjects randomized in Phase 2. In the interim, a Data Review Committee consisting of experts internal and external to Janssen will monitor Phase 2 data on an ongoing basis.

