17.9. Study Completion/Termination

17.9.1. Study Completion/End of Study

The end of the study is defined as the last study assessment for the last subject on study or anytime the sponsor terminates the study, whichever comes first.

Prior to Protocol Amendment 5, the final data from the study-site was to be sent to the sponsor (or designee) after completion of the final subject visit at that study-site, in the time frame specified in the clinical trial agreement.

Following Amendment 5, the end of study data collection is defined as when the primary efficacy analysis clinical cutoff has been achieved. At that time, follow up of subjects will end and the eCRF will be closed. Subjects who are continuing to derive benefit from erdafitinib and/or cetrelimab treatment as assessed by their investigator may continue to receive erdafitinib and/or cetrelimab; during this period, only serious adverse events will be monitored and entered into the Company safety repository.

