Disease assessment and response evaluation	Radiologic assessment by CT (preferred) or MRI of all disease sites (present and suspected) documented at Screening. The same methodology should be used throughout the study. Refer to		X						Every 6 weeks until Week 48 (±3 days), then every 12 to 24 weeks (±14 days) until disease progression. The timing of disease assessments should be calculated from C1D1 and the schedule should be maintained regardless of cycle delays and/or study drug interruptions. For subjects who discontinue study drug before disease progression, tumor assessments should continue as scheduled (see Section 9.1.3). Tumor response will be evaluated according to RECIST 1.1 criteria (Seymour 2017). All unconfirmed PR/CR require confirmation of response as per RECIST 1.1.		

Assessments/ Procedure	Notes	Molecular Eligibility Screening Period	Full-Study Screening Period	Treatment Cycle 1 ^g		Treatment Cycle 2 ^{g, 3}		All Other Cycles ^g		End-of-Treatment ^{a, g}	Follow-up Period ^{a, g}
		≥28 days prior to C1D1	Within 28 days prior to C1D1	Day 1	Day 15 (±2)	Day 1 (±2)	Day 15 (±2)	Day 1 (±2)	Day 15 (±2) ^f	Within 30 Days (+7) of last dose	Every 12 weeks
	Section 9.2. for details. Disease assessments done within 35 days prior to C1D1 may be used as the Screening disease assessment.										
Ongoing Review											
Adverse Events	X - Continuous from signing of Full-Study ICF to up to 100 days after the last dose of study treatment or until the start of subsequent anticancer therapy. An AE should be monitored until it resolves to baseline, stabilizes, or is deemed irreversible, subject dies, or subsequent therapy is started, whichever occurs first.										
Concomitant medications	X - Continuous from signing of Full-Study ICF to up to 100 days after the last dose of study treatment or until the start of subsequent anticancer therapy, if earlier. See Section 8.										
Posttreatment Assessments											
Survival evaluation	Contact subject every 12 weeks (±7 days) after the last dose of study treatment by office visit, phone call or e-mail. See Section 9.1.4.										X
Subsequent anticancer therapy	Contact subject every 12 weeks (±7 days) after the last dose of study treatment by office visit, phone call or e-mail. See Section 9.1.4.										X

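### The only efficacy cutoff can be brought forward when the single last-enrolled subject discontinues, leaving other recent enrollees in the ORR denominator too early to count as confirmed responders

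*Protocol*

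**What the plan says.** Section 11.4 plans the primary efficacy analysis at about "6 months of follow-up from last patient enrolled or sooner (if last patient discontinued prior to the 6-month follow-up") and states that it is the final analysis. The Statistical Methods part of the Synopsis carries the same rule: "The primary efficacy analysis is planned with ~6 months of follow-up from last patient enrolled or sooner", with the same exception in parentheses. Section 17.9.1 defines the end of data collection as this cutoff and adds: "At that time, follow up of subjects will end and the eCRF will be closed". After that only serious adverse events are recorded, in the safety repository.

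Other provisions that bear on the point:

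- **Scans and confirmation.** Appendix 3 Table 1 schedules imaging every 6 weeks from C1D1 to Week 48 and says: "All unconfirmed PR/CR require confirmation of response as per RECIST 1.1".
- **Denominator.** Section 11.4 analyses ORR by arm in the treated population, which Section 11.3 defines as anyone who received at least one dose. Section 11.3 adds: "The Treated Population will be used for all safety analyses and for efficacy analysis unless otherwise specified in the Statistical Analysis Plan".
- **Meaning of discontinued.** Section 10.2 uses discontinuation for stopping treatment and withdrawal for leaving the study. Of the former it says: "A subject who discontinued treatment will be followed up for recovery of AEs for subsequent therapies and survival".
- **A second trigger.** Section 1.7 says: "Analyses of safety and efficacy will be performed by each arm when there are approximately 90 response-evaluable subjects randomized in Phase 2".

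**The concern.** The exception looks at one subject only. If that subject stops early, the sponsor may cut the data for everyone, although others enrolled in the preceding weeks may be on treatment and not yet have reached the scan that could confirm a response. They remain in the ORR denominator and generally cannot be in the numerator, so the primary efficacy endpoint is pulled down. No later analysis is planned to correct it.

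The trigger is also unclear. If discontinued means off treatment, Section 10.2 keeps that subject in follow-up and Section 9.1.3 continues imaging until progression, so even the triggering subject may still have data to give.

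DoR, PFS and OS would lose precision and maturity, but earlier Kaplan-Meier censoring does not in itself bias them.

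**Working it through.** **The plan's own figure.** With 45 subjects per arm, the Wald interval is p ± 1.96 × √(p(1 − p)/45).

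- Arm A, p = 0.45: 0.45 ± 0.145, or 30.5% to 59.5%.
- Arm B, p = 0.55: 0.55 ± 0.145, or 40.5% to 69.5%.

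Both agree with Section 11.1.2. The half-width, about 14.5 points, is the yardstick below.

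**Time needed for a confirmed response.** With scans at Weeks 6, 12, 18 and so on, a response first seen at Week 6 is confirmed at Week 12 at the earliest scheduled scan. A cutoff at 6–11 weeks gives a subject one scheduled scan, at 12–17 weeks two, and at 24–26 weeks four.

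**How often the clause could fire.** The protocol gives no discontinuation rate, so medians from Study BLC2001 serve as proxies, with exponential times: P(T < t) = 1 − 0.5^(t/m). Six weeks is 1.38 months and 12 weeks is 2.76 months.

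| Proxy for the last subject's event | Median m (months) | Before 6 months | Before 12 weeks | Before 6 weeks |
|---|---|---|---|---|
| Treatment duration (Section 1.3; mostly chemo-refractory) | 5.4 | 54% | 30% | 16% |
| First-line PFS (Section 1.7; n = 10) | 9.82 | 35% | 18% | 9% |
| OS, 8 mg regimen (Section 1.3) | 11.3 | 31% | 16% | 8% |
| First-line OS (Section 1.7) | 18.14 | 20% | 10% | 5% |

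The first two rows stand for the off-treatment reading. The first-line figure comes from this statement: "In these 10 patients, median progression-free survival was 9.82 months". The last two rows apply if only death counts.

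**Effect on ORR.** Simulation with 20,000 trials per setting. Assumptions: 90 subjects, uniform accrual, true ORR 50%, first response at Week 6, 12 or 18 in 70%, 20% and 10% of responders, confirmation 6 weeks later, and the cutoff taken on the day the last subject's event occurs. The loss is confirmed ORR at last enrolment plus 6 months, minus confirmed ORR at the earlier cutoff, in percentage points.

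| Accrual (months) | 12 | 18 | 24 | 36 | 45 |
|---|---|---|---|---|---|
| Mean loss when fired, m = 5.4 | 5.4 | 3.7 | 2.9 | 2.0 | 1.7 |
| Mean loss when fired, m = 9.82 | 4.9 | 3.4 | 2.6 | 1.8 | 1.5 |
| Mean loss if fired within 6 weeks, m = 5.4 | 11.6 | 7.9 | 6.1 | 4.2 | 3.5 |
| Mean loss over all trials, m = 5.4 | 2.9 | 2.0 | 1.5 | 1.1 | 0.9 |
| Mean loss over all trials, m = 9.82 | 1.7 | 1.2 | 0.9 | 0.6 | 0.5 |

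On the off-treatment reading, about 2–7 subjects across both arms have under 12 weeks of follow-up when the clause fires, and about 5–17 when it fires within 6 weeks. On the death-only reading, the loss over all trials is 0.3–1.5 points.

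**The case against.** The strongest case against concerns size.

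- **Harm is concentrated early.** Everyone else was enrolled before the last subject, so their potential follow-up is at least as long. When the clause fires at or after Week 12, the mean loss is only 0.3–0.9 points. The relevant probability on the off-treatment reading is therefore nearer 18–30% than 35–54%. This stands.
- **The clause permits an early cutoff; it does not require one.** The simulation uses it every time and on the exact day, so the averages over all trials are an upper reading. This stands.
- **Accrual was probably slow.** Section 1.5.2 dates the scheduled review of the first 20 randomized subjects to 11 September 2020. Losses at the upper end need 12-month accrual; at 36–45 months the average is 0.5–1.1 points on the off-treatment reading.
- **If discontinued means leaving the study,** Section 10.2 limits that to loss to follow-up or withdrawn consent. That is probably rarer than any event modelled here, and no figure is available for it.
- **Phase 2 estimates each arm separately,** without a hypothesis test. The bias is conservative, and one cutoff applies to both randomized arms.
- **The SAP may name another efficacy population,** as Section 11.3 allows. It is not at hand. Section 11.4 nevertheless fixes the cutoff, the treated population and the end of efficacy data collection itself, so this is a stated rule rather than a detail left for later.

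It could also be argued for the concern that the Wald lower limits clear 30% and 40% by only about 0.5 points, so one immature subject per arm would undo them. That carries no weight here: the narrow margin belongs to the sample-size statement and exists without the clause.

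**Conclusion.** The concern holds. As written, one subject's undefined discontinuation may set the only efficacy cutoff, with no floor on follow-up for other recent enrollees and no planned update. The resulting error in ORR is downward.

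Its expected size is modest: 0.5–2.9 points over all trials on the off-treatment reading and 0.3–1.5 if only death counts, both assuming the option is always used. The loss would matter in one trial if the last subject stopped within 6 weeks: about 3.5–11.6 points, with 5–16% probability across the proxies. The event-time medians come from another study, while accrual, response timing and the exponential form are assumptions. None of these is data from this trial.

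The different trigger in Section 1.7 is a genuine inconsistency but an editorial one; it adds nothing to the bias argument. The change should be made because it is cheap and protects the primary endpoint.

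**What to change.** In Section 11.4 and the Synopsis, delete the exception that allows an earlier analysis when the last subject discontinues. Define the cutoff instead as the date on which every treated Phase 2 subject has at least 6 months of follow-up from C1D1, or has progressed, died, withdrawn consent or been lost to follow-up. Replace the trigger in Section 1.7 with the same rule.

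This date cannot fall later than 6 months after the last subject's C1D1, so no single subject can delay it. It still allows an earlier cutoff when every subject short of 6 months has reached one of those events. It also removes the undefined term.

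The cost is wording, plus at most a few months of already scheduled follow-up compared with an early cutoff. No extra subjects or procedures are needed.
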